## 1.0 Objectives / Specific Aims

### Specific Aim 1

The goal of Specific Aim 1 is to develop an effective remote mental health and substance use Screening, Brief Intervention and Referral to Treatment (SBIRT) program for pregnant and postpartum women. The **objectives** of this current application for Specific Aim 1 are to conduct a pilot RCT of a text-message based SBIRT and home-based telemedicine services for pregnant and postpartum women – called Listening to Women (LTW), compared to treatment as usual (TAU) with the primary objective to provide effect size estimates for a larger RCT.

**Specific Aim 1:** Conduct a pilot, small-scale randomized controlled trial to examine feasibility and preliminary efficacy of LTW, compared to TAU. Outcomes related to feasibility include percentage of eligible patients recruited, **study attrition**, **study retention**, and mental health and substance use treatment appointment attendance. Outcomes related to **preliminary efficacy** will include participation in screening, referral and treatment at baseline, compared to TAU.

The central hypotheses for Specific Aim 1 are that the study is feasible and women assigned to LTW will be more likely to screen positive and successfully obtain treatment in less time, compared to those that are assigned to TAU.

### Specific Aim 2

Upon completion of Specific Aim 1, the goal of Specific Aim 2 is to evaluate the effectiveness of a remote mental health and substance use Screening, Brief Intervention and Referral to Treatment (SBIRT) program for pregnant and postpartum women. The **objectives** of this current application for Specific Aim 2 are to conduct an RCT of a text-message based SBIRT and home-based telemedicine services for pregnant and postpartum women – called Listening to Women (LTW), compared to treatment as usual (TAU) with the primary objective to include attendance to treatment at baseline, compared to TAU.

**Specific Aim 2:** Conduct a randomized controlled trial to examine the effectiveness of LTW, compared to TAU. Outcomes related to **effectiveness** include attendance to treatment at baseline, compared to TAU.

The central hypotheses are that a greater proportion of women assigned to LTW will attend treatment following a referral, compared to TAU.

### Specific Aim 3

The goal of Specific Aim 3 is to gather data related to maternal and newborn diagnosis codes, health care utilization, and costs for our study participants with Medicaid.

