To address these barriers we designed, implemented and piloted LTW in routine perinatal care in one obstetric practice (see 3.0 Intervention to be Studied) as part of a quality improvement project. Our pilot demonstrates high rates of participation with 87.78% (273/311) of women approached agreeing to take part in LTW and completing the text-message screening. Preliminary data comparing LTW (N=273) to a historical dataset extracted from the EHR including peripartum women receiving in-person SBIRT in the same clinic (N=2,988) found a significantly greater proportion of women enrolled in LTW screened positive (81.15% vs. 33.33%;  $\chi^2=169.50$ ,  $p<0.0001$ ), were referred for treatment (76.12% vs. 57.63%;  $\chi^2=18.03$ ,  $p<0.0001$ ), and received treatment (94.91% vs. 16.04%;  $\chi^2=245.41$ ,  $p<0.0001$ ), compared to women receiving in-person SBIRT.

While these preliminary data are exciting, a randomized control trial will be necessary to determine the feasibility and efficacy of LTW. The goal of Specific Aim 1 is to examine the feasibility and preliminary efficacy of the proposed RCT methodology. Specific Aim 1 will inform Specific Aim 2 to then conduct a larger-scale RCT that examines LTW, compared to a control condition. This will allow us to identify and address barriers in recruitment, retention, use of LTW, and other procedures essential to successful conduct of the RCT. This approach is consistent with expert recommendations to use pilot mechanisms to test the feasibility of doing a full-scale RCT, use data yielded by the pilot study to “de-bug” the methodology, and to assess optimal strategies to executing the RCT [51- R34].

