## 4.0 Study Endpoints

### Specific Aim 1:

#### **Primary pilot efficacy outcome variables include:**

Completion of SBIRT: We will compare the proportion of participants that complete a screen for mental health and substance use, the proportion of those screening positive that are referred to treatment, and the proportion of those referred to treatment that had at least one mental health and/or substance use disorder treatment appointment among those assigned to LTW, compared to TAU.

Time to Treatment: We will measure the time from completion of screening positive to time of first mental health or substance use treatment appointment (if a referral to treatment was appropriate) among those assigned to LTW, compared to TAU.

Reduction in Mental Health Symptoms: Among women referred for treatment, we will compare the mean change in the Edinburgh Postnatal Depression Scale (EPDS) among those assigned to LTW, compared to TAU. *Of note, the suicidal ideation question (item #10) will be omitted from this questionnaire.*

Reduction in Substance Use: Among women referred for treatment, we will compare change in substance use frequency and amount as measured by the NIDA-Modified Assist (see LTW protocol) among those assigned to LTW, compared to TAU.

Improved Maternal Functioning: Among women referred for treatment, we will compare the change in maternal functioning measured by the Medical Outcomes Study Short Form 36 (SF-36v2) among those assigned to LTW, compared to TAU.

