**Specific Aim 2:**

**Primary Outcome:**

Attendance to Treatment: treatment attendance (defined as attending at least 1 or more visits with a mental health and/or substance use disorder (SUD) treatment provider during pregnancy and the postpartum year)

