## **6.0 Number of Subjects**

A total of 450 participants will be randomized in Specific Aim 1 (n=100) and Specific Aim 2 (n=350). To randomize 450 participants we will need to approach about 1,500 participants in order to get to 450 total participants.

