## **10.0 Study Design / Methods**

Specific aim 1: A two arm pilot RCT (N=100) with 2:1 allocation will examine feasibility and preliminary efficacy of LTW, compared to TAU. Specific aim 2: A RCT (N=350) with 2:1 allocation will examine effectiveness of LTW, compared to TAU. As of the approval of amendment #12 the allocation will switch to 1(LTW):2(TAU) for specific aim 2. Recruitment will primarily occur proactively and remotely via the EHR. We will conduct a weekly EHR search via a recruitment report for all new pregnant and postpartum patients in the past week. The report will include mrn, age, race, ethnicity, date of prenatal care visit, date of postpartum visit, delivery date, ob/gyn provider name, MyChart account (Yes/No), cell phone number, email address and current ICD-9 or 10 diagnoses. Any patients who have not opted out of being contacted for research will be contacted and invited to participate. The study team will not cold-contact any patients who have chosen to opt-out of receiving contact about research or who have met the maximum number of contact attempts at the time of recruitment. If the potential participant has not opted out of being contacted, or the potential participant's provider has agreed to have the study team contact their patient, a phone call will be made or message will be sent via text, email or MyChart message to the potential participant inviting them to take part in the study. This invitation will include clear opt out procedures should the patient not wish to be contacted in the future for the purpose of this study. If interested, participants will complete a screening online via REDCap to determine study eligibility (see above for inclusion criteria). After completing preliminary determination of eligibility, if eligible and interested in participating in the study, participants will be scheduled for a time to complete informed consent (see 9.0 Consent Process).

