Statistical Analysis Plan

Sample Size and Power Analysis

Using a chi-square testing framework and a significance level of 0.05 and assuming two-sided hypothesis testing, both primary and secondary outcomes included a large enough sample size to detect differences between groups. Our a priori group sample sizes (usual care: n=191; LTWP: n=224) provided 80% power to detect between-group absolute differences in proportions ranging from 6% to 12% in the primary study outcomes (for example, screened: 65.2% [usual care] versus 77.7% [LTWP]; screened positive: 21.7% versus 34.2%, respectively; referred: 12.5% versus 23.1%, respectively; and attended treatment: 2.1% versus 8.3%, respectively). Our group sample sizes among participants completing a screen (usual care: n=63; LTWP: n=221) provided 80% power to detect between-group absolute differences in proportions ranging from 11% to 18% in the secondary study outcomes (for example, screened positive: 17.5% [usual care] versus 35.4% [LTWP]; referred: 3.2% versus 15.3%, respectively; and attended treatment: 1.6% versus 12.3%, respectively). The usual care rates used in these calculations were based on data published from earlier work on the LTWP program.

Data Analysis

We will assess the adequacy of randomization by comparing LTWP versus usual care (UC) on demographic, obstetric, and psychiatric baseline characteristics, using t-tests or Wilcoxon rank sum tests for continuous variables and chi-square tests or Fisher's exact tests for categorical variables, respectively. Descriptive statistics will be calculated for each screening method (LTWP versus usual care), including counts and percentages for participants who were screened, screened positive, referred to treatment, and attended treatment. Unadjusted differences in outcomes between people assigned to LTWP versus UC will be calculated using chi-square tests because all study outcomes are dichotomous. Relative risk (RR) ratios will be estimated and reported along with their 95% confidence intervals. All hypothesis tests will be two-sided with a type 1 error set at 0.05, and all analyses will be performed using SAS statistical software, version 9.4 (Cary, NC).

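### The SAP makes four outcomes primary and powers them on an unexplained 415 women; the protocol gives Aim 2 one primary outcome, treatment attendance, and 350 women

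*SAP*

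**What the plan says.** **Protocol.** Section 4.0 lists a single item under the Aim 2 primary outcome: "Attendance to Treatment: treatment attendance (defined as attending at least 1 or more visits", counted over pregnancy and the postpartum year. It gives no denominator. Section 1.0 describes the same outcome differently. The Aim 2 objective reads "with the primary objective to include attendance to treatment at baseline, compared to TAU", and the hypothesis is that "a greater proportion of women assigned to LTW will attend treatment following a referral". The earlier steps of the pathway are primary only under Aim 1, in the item that begins "Completion of SBIRT: We will compare the proportion of participants that complete a screen for mental health and substance use" and goes on to referral among those screening positive and attendance among those referred.

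On numbers, section 6.0 says "A total of 450 participants will be randomized in Specific Aim 1 (n=100) and Specific Aim 2 (n=350". Section 10.0 starts Aim 2 at 2:1, then says "As of the approval of amendment #12 the allocation will switch to 1(LTW):2(TAU) for specific aim 2".

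**SAP.** The section on sample size and power names no aim. With 191 usual-care and 224 LTW women it claims "80% power to detect between-group absolute differences in proportions ranging from 6% to 12% in the primary study outcomes" and gives four examples:
- screened, 65.2% v 77.7%
- screened positive, 21.7% v 34.2%
- referred, 12.5% v 23.1%
- attended treatment, 2.1% v 8.3%

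The last three appear again as secondary outcomes among screen completers (63 and 221). The Data Analysis section lists the same four outcomes side by side, compares the arms by chi-square, and sets every test at two-sided 0.05.

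**The concern.** Aim 2 asks whether more women reach treatment. LTW changes how screening is delivered, so screening steps may move even if attendance does not. The SAP labels all four steps primary and does not say which one carries the conclusion. A significant result for screening could then be presented as a primary success of the effectiveness trial alongside a non-significant attendance result, and no written rule would say otherwise.

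The power statement has a related problem. It is attached to 415 women, and neither document says whether these are Aim 2 women, both aims pooled, or something else. The reader cannot tell whether the 80% describes the trial that will be analysed.

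**Working it through.** **1. Reproduce the SAP's 80%.** The inputs are the SAP's group sizes and rates, two-sided 0.05. The chi-square power formula is

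Power = Φ[(|p2 − p1| − 1.96·s0) / s1], where s0 = √[p̄(1 − p̄)(1/n1 + 1/n2)], s1 = √[p1(1 − p1)/n1 + p2(1 − p2)/n2], and p̄ is the weighted mean rate.

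Attendance, 191/224:
- p̄ = (191 × 0.021 + 224 × 0.083)/415 = 0.0545
- s0 = 0.02235 and s1 = 0.02115
- (0.062 − 1.96 × 0.02235)/0.02115 = 0.860, and Φ(0.860) = 80.5%

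| Outcome | Formula | Exact |
|---|---|---|
| Screened | 80.6% | 81.0% |
| Screened positive | 80.8% | 81.1% |
| Referred | 80.3% | 80.9% |
| Attended | 80.5% | 83.4% |

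Exact means enumeration of the uncorrected chi-square test. The SAP's arithmetic is sound.

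**2. Compare the totals.** 191 + 224 = 415. That is 315 more than Aim 1 (100), 65 more than Aim 2 (350) and 35 fewer than the two combined (450).

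**3. False-positive risk if any one of four counts.** The outcomes are nested, so independence would overstate the risk. I simulated 1,000,000 trials at 191/224 with the usual-care rates in both arms. Each step was drawn from the women who reached the step before, with conditional rates 21.7/65.2 = 33.3%, 12.5/21.7 = 57.6% and 2.1/12.5 = 16.8%. These lie close to the historical in-person rates in protocol section 2.0 (33.33%, 57.63%, 16.04%), which supports reading the SAP rates as a nested chain over all women.

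| | Two-sided | Favouring LTW |
|---|---|---|
| Attendance alone | 4.2% | 2.0% |
| At least one of four | 15.6% | 7.7% |

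The nominal level per test is 5% two-sided and 2.5% in one direction.

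**4. Attendance power under each possible analysis set**, at 2.1% v 8.3%. The number of women enrolled before amendment 12 is not given. I read the first ratio as 2 LTW : 1 TAU, since the amendment reverses it. If k of the 350 were randomised before the switch, LTW has 2k/3 + (350 − k)/3 = (350 + k)/3 women. The splits below run from k = 262 to k = 88, that is, 75% to 25% of Aim 2 enrolled before the switch. This range is an assumption.

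| Analysis set (usual care/LTW) | Formula | Exact | Detectable difference from 2.1%, 80% power by formula |
|---|---|---|---|
| SAP, 191/224 | 80.5% | 83.4% | 6.1 points |
| Aim 2 alone, 146/204 | 71.2% | 74.9% | 7.1 points |
| Aim 2 alone, 175/175 | 74.5% | 77.4% | 6.8 points |
| Aim 2 alone, 204/146 | 75.3% | 78.9% | 6.7 points |
| Pooled 450 in the SAP's ratio, 207/243 | 83.7% | 86.7% | 5.8 points |

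**The case against.** The best defence is that protocol section 4.0 already names attendance as Aim 2's primary outcome and that its test at 0.05 is not inflated by testing other steps. That is correct. The any-of-four figure also assumes a success rule that the SAP does not contain, and about half of the 15.6% favours usual care. So 7.7% is the relevant number, and it is conditional on that rule. What remains is that the SAP calls all four primary and nothing in it prevents that reading. The words introducing the rates as examples do not help, because no other primary outcomes are named.

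Several stronger readings are tempting, and the documents do not support them:

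- **That the trial is underpowered.** Since 415 exceeds 350, the SAP's set cannot be Aim 2 alone at its planned size. The shortfall is one branch; pooling at 450 gives more than 80%. Even in the Aim 2 branch, the detectable difference grows by at most one point.
- **That power collapses because attendance is judged only among referred women.** The hypothesis wording allows the thought, but it can equally describe a sequence among women assigned to LTW. The SAP powers attendance among all women and, as secondary, among screen completers. It plans no referred-only analysis for Aim 2.
- **That a significant earlier step alongside non-significant attendance is a false positive.** If LTW really improves screening, that result is true. The fault would lie in labelling it the primary answer to Aim 2.

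One could also say the SAP serves Aim 1. But Aim 1 has 100 women, its referral and attendance proportions are conditional on the previous step, and screened positive is not among its listed primary proportions. The SAP's set fits neither aim as written.

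**Conclusion.** The mismatch stands and should be settled before outcomes are compared by arm. The protocol gives Aim 2 one primary outcome and 350 women; the SAP gives an unnamed aim four unranked primary outcomes and 415 women.

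The consequence for inference is that the primary conclusion is not fixed in advance. If any one of the four sufficed, the chance of a false positive for LTW would be about 7.7% rather than 2.5%. This assumes a global null, nested outcomes and the SAP's usual-care rates. The error rate of the attendance test itself is unaffected.

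The consequence for power is modest and can go either way: about 71–75% by formula (75–79% exact) for Aim 2 alone over the assumed splits, or about 84% (87% exact) if pooled at 450. The SAP's 80% is right for the numbers it uses. What is missing is the link between those numbers and the protocol.

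**What to change.** In the SAP:

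1. State which aim the plan serves and whether the analysis set is Aim 2 alone or Aims 1 and 2 pooled. Explain how 191 and 224 arise. If the aims are pooled, say so in the protocol as well.
2. For Aim 2, name treatment attendance as the sole primary outcome, tested at two-sided 0.05 among all randomised women. This is the denominator of the SAP's own primary calculation. Keep screen completers as the secondary set.
3. Make screened, screened positive and referred secondary for Aim 2. Those that section 4.0 lists for Aim 1 may stay primary there.
4. Restate the attendance power, or the detectable difference, for the analysis set chosen and its actual split between arms.

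In the protocol, reconcile the two phrases in section 1.0 (attendance at baseline, and attendance following a referral) with the pregnancy and postpartum-year window in section 4.0, and add the denominator.

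The cost is a revised SAP section and a few protocol sentences, with no new data. The earlier steps lose primary status for Aim 2, and the stated power may be slightly lower if Aim 2 is analysed alone.

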## 3.0 Intervention to be studied

LTW is a mobile phone-based program designed to enhance delivery of Screening, Brief Intervention, and Referral to Treatment (SBIRT), an evidence-based approach for mental health and substance use screening

and treatment for perinatal women [36-38]. This program was created as a result of key informant interviews with obstetric providers and pregnant and postpartum women with opioid use disorders. Feedback from these groups informed the development of LTW.

The program utilizes mobile phone text message-based screenings with immediate automated feedback, paired with remote care coordination and, if appropriate, home-based telemedicine mental health and substance use disorder treatment services. Women coming into routine prenatal care (see Recruitment) are eligible to take part in the study. Those agreeing to take part are sent a text message with routine mental health and substance use screening questions (see LTW protocol for screening questions) currently employed as part of standard of care. These screening questions are the SBIRT which is a survey with 9 questions related to depression, anxiety, substance abuse (alcohol, cigarettes, other drugs including prescription medication), and domestic violence (see LTW protocol). However, LTW uses text-message based screening with phone based assessment and referral to treatment, and TAU is an in-person screening and referral to treatment assessment. The same screening tools are used to assess substance abuse and mental health problems in LTW and TAU. Once they complete these screenings via text message, they are provided immediate feedback about their scores, and recommendations (see LTW protocol for automated messages). Contact information for the study's care coordinator is also provided along with her availability i.e., Monday – Friday 8am-5pm. In addition, while specific questions about suicidal ideation are not asked via the text message screening, all participants receive a text message: "If you are ever experiencing a mental health emergency, such as a desire to harm yourself or others, please go to your nearest emergency room. If you are feeling suicidal you can call the National Suicide Prevention Lifeline [name] anytime" (see LTW protocol for automated messages).

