#### **Protections Against Loss of Confidentiality**

All screening information will be kept in a password protected REDCap database. Only key study personnel will have access to the database. If an individual is not eligible to participate based on her answers to the eligibility survey, her screener will not include her name or contact information. Only people who meet eligibility criteria based on the answers to the eligibility survey will be asked if they would like to be contacted about participation in the study and for their name and contact information. Eligible participants' full name, telephone number and

e-mail address will be recorded in the study enrollment log located on a secure MUSC drive or in MUSC Box. The REDCap database and the study enrollment log are the only places where participants' names and subject identification numbers appear together. Eligible participants will be assigned a subject number, will complete informed consent, will be randomized, will complete baseline assessments, and subsequently will receive their randomized intervention.

Upon completing eligibility screening, if study eligible, individuals will be provided with an overview of the study, asked to review study procedures via a consent form, and asked to provide signed consent. Participants will be informed of limitations of confidentiality (i.e., abuse or neglect, intention to harm self or someone else) both verbally and/or in writing during the informed consent process. The consent form will include the participant's name, but not his/her subject number. Consent forms will be provided in English.

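### The SAP tests its secondary outcomes only among women who completed a screen, a group formed after randomisation by the step LTW is meant to change

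*SAP*

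**What the plan says.** The SAP's Sample Size and Power Analysis section gives two sets of group sizes. The primary outcomes (screened, screened positive, referred, attended) use the larger groups: "Our a priori group sample sizes (usual care: n=191; LTWP: n=224) provided 80% power". The secondary outcomes are the last three of these again, restricted to completers: "Our group sample sizes among participants completing a screen (usual care: n=63; LTWP: n=221) provided 80% power". The secondary example rates, usual care against LTWP, are 17.5% and 35.4% positive, 3.2% and 15.3% referred, and 1.6% and 12.3% attended.

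The Data Analysis section has one rule for everything: "Unadjusted differences in outcomes between people assigned to LTWP versus UC will be calculated using chi-square tests because all study outcomes are dichotomous". Relative risks with 95% confidence intervals and a two-sided 0.05 level follow. It does not repeat the completer restriction, name an analysis population for any outcome, or attach a caveat to the secondary results.

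The protocol places screening after allocation and inside the intervention. Women "will be randomized, will complete baseline assessments, and subsequently will receive their randomized intervention" (Protections Against Loss of Confidentiality). Section 3.0 says that "LTW uses text-message based screening with phone based assessment and referral to treatment, and TAU is an in-person screening". Section 4.0 makes completion an Aim 1 primary pilot efficacy outcome: "We will compare the proportion of participants that complete a screen for mental health and substance use". The same paragraph then compares referral among women who screened positive, and attendance among women who were referred.

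**The concern.** Randomisation makes the arms comparable as assigned. It does not make screened women in one arm comparable with screened women in the other when the arm affects who is screened. Here the arms differ in how the screen is delivered, and completion is expected to differ. Usual-care completers may be healthier or sicker than LTWP completers before any referral takes place.

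A p-value and relative risk among completers, reported by assigned arm with no qualification, would be read as an effect of LTW. It could overstate or understate that effect. The stepwise proportions in protocol section 4.0 have the same structure, with further selection at each step.

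**Working it through.** **1. The plan's own figure.** Power = Φ[(|p2 − p1| − 1.96·SE0)/SE1], where SE0 uses the pooled proportion, SE1 the separate proportions, and n = 63 and 221. For screened positive, the pooled proportion is (63 × 0.175 + 221 × 0.354)/284 = 0.314, SE0 = 0.0663 and SE1 = 0.0577. Power = Φ[(0.179 − 0.130)/0.0577] = 80.2%. Referred and attended each give 80.4%. The stated 80% is right; the problem is which women are compared.

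**2. Share of each arm compared.** This assumes that 63 and 221 are subsets of 191 and 224, which the SAP's wording suggests but does not say.
- Usual care: 63/191 = 33.0%, so 128 women are left out.
- LTWP: 221/224 = 98.7%, so 3 are left out.

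**3. What the completer data can say about women who would be screened in either arm.** Assume also that LTW never prevents a screen, and take the SAP's example rates. The share of LTWP completers who would also have been screened under usual care is 0.3298/0.9866 = 0.334, so 66.6% are trimmed. The LTWP rate in that group lies between max[0, (p − 0.666)/0.334] and min[1, p/0.334]. Subtracting the usual-care rate gives:

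| Outcome | LTWP rate, bounds | Usual care | Difference (points) |
|---|---|---|---|
| Screened positive | 0 to 100% | 17.5% | −17.5 to +82.5 |
| Referred | 0 to 45.8% | 3.2% | −3.2 to +42.6 |
| Attended | 0 to 36.8% | 1.6% | −1.6 to +35.2 |

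All three include zero, before sampling error.

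**4. Error rate of the planned test under selection alone.** Suppose 35.4% of all women in each arm would screen positive, so there is no true difference, and hold LTWP completers at 35.4% because 98.7% of that arm completes. The usual-care completer rate pc then solves 0.3298·pc + 0.6702·pu = 0.354, where the unscreened women's odds of positivity, pu/(1 − pu), are OR times those of the completers. Rejection of the uncorrected chi-square test at n = 63 and 221 comes from exact binomial enumeration.

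| Odds of positivity, unscreened against screened usual care | pc | Rejection |
|---|---|---|
| Equal | 35.4% | 5.0% |
| 1.5 times higher | 29.3% | 13.9% |
| 2 times higher | 25.3% | 31.9% |
| 3 times higher | 20.1% | 65.3% |
| 1.5 times lower | 41.7% | 15.5% |
| 2 times lower | 46.2% | 35.0% |
| 3 times lower | 52.6% | 69.0% |

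Selection alone would reproduce the SAP's 17.5% in usual care if pu = (0.354 − 0.3298 × 0.175)/0.6702 = 44.2%, an odds ratio of about 3.7. The test then rejects about 80% of the time. No passage supports any particular odds ratio.

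**5. A mismatch in the SAP's inputs.** The primary example takes 65.2% screened in usual care, and the SAP says: "The usual care rates used in these calculations were based on data published from earlier work on the LTWP program". Applied to 191 women this gives 0.652 × 191 = 124.5 screened, against 63 stated.

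**The case against.** **The size depends on the subset reading.** The SAP's only stated screening rates are 65.2% and 77.7%. With those as completion rates, trimming falls to 1 − 0.652/0.777 = 16.1%, and the bounds for screened positive become +5.5 to +24.7 points, which exclude zero. Referred (−3.2 to +15.0) and attended (−1.6 to +13.1) still include it. Rejection at odds ratios of 1.5, 2 and 3 falls to 7.4%, 12.6% and 25.3%. But these rates do not fit the stated groups: 221 completers at 77.7% would need 221/0.777 = 284 LTWP women, against 224. The sensitivity to the completion gap is real, so the figures above are illustrations and not estimates. It is also fair that bounds including zero are nearly automatic when two thirds of an arm is trimmed, and that 35.4% is itself a power-calculation value.

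**The sound analysis is already planned.** The same three outcomes are primary on 191 and 224, and the Aim 2 primary outcome in protocol section 4.0 does not require a screen. This stands. It confines the fault to the secondary results and makes the fix cheap, but it does not make those results randomised comparisons.

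**The stepwise proportions belong to a pilot.** They do, so that part carries less weight. But the pilot is meant to supply effect sizes for the larger trial, and conditional ones carry the same selection forward.

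**Counting unscreened women as not positive changes the question.** It does. Under the subset assumption, the SAP's rates imply 11 and 78 positives. The relative risk is (78/221)/(11/63) = 2.0 among completers and (78/224)/(11/191) = 6.0 among all assigned, and the second partly reflects screening itself. The two answer different questions, so the gap does not show which way selection runs. Only the second compares randomised groups.

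**Conclusion.** The concern holds and should be fixed. That the completer groups are not randomised groups follows from the design and needs no assumed number. The sizes do need assumptions. The 33.0% and 98.7% rest on the completers being subsets of 191 and 224. The bounds add monotone screening and the SAP's example rates. The rejection rates, 13.9% to 65.3% in one direction and 15.5% to 69.0% in the other, rest on hypothetical odds ratios of 1.5 to 3. The direction of bias cannot be determined from the documents. The primary comparisons on the full groups do not have this problem; nothing here vouches for other aspects of those groups.

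**What to change.** In the SAP's Data Analysis section:
- State the analysis population for each outcome, and base all between-arm tests and relative risks on the full assigned groups.
- Apply the 'no' rule outcome by outcome: a woman not screened is not screened and not screen-positive, one with no referral is not referred, and one with no recorded visit has not attended. A woman who attends without a screen still counts as attending.
- Present completer-only results as conditional, non-randomised and descriptive or exploratory, not as treatment effects.

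In protocol section 4.0, use all randomised women as the denominator when the arms are compared on referral and attendance, and keep the stepwise proportions as description.

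Reconcile the 65.2% usual-care screening rate with 63/191 = 33.0%, and say whether the 63 and 221 are subsets of the 191 and 224. The 77.7% is a detectable-difference value and needs no reconciling.

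The cost is wording, with no new data. The downside is that comparisons of yield per completed screen lose their inferential status.
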